9.1. Efficacy Assessments

This section is not applicable for this study.

9.2. Adverse Events

Investigators are responsible for monitoring the safety of subjects who have entered this study and for alerting Lilly or its designee to any event that seems unusual, even if this event may be considered an unanticipated benefit to the subject.

The investigator is responsible for the appropriate medical care of subjects during the study.

Investigators must document their review of each laboratory safety report.

The investigator remains responsible for following, through an appropriate health care option, AEs that are serious or otherwise medically important, considered related to the investigational product or the study, or that caused the subject to discontinue the investigational product before completing the study. The subject should be followed up until the event resolves, stabilizes with appropriate diagnostic evaluation, or is reasonably explained. The frequency of follow-up evaluations of the AE is left to the discretion of the investigator.

The investigator will record all relevant AE and SAE information in the eCRF. After the informed consent form (ICF) is signed, study site personnel will record, via eCRF, the occurrence and nature of each subject's preexisting conditions, including clinically significant signs and symptoms of the disease under treatment in the study. Additionally, site personnel will record any change in the condition(s) and the occurrence and nature of any AEs.

The investigator will interpret and document whether an AE has a reasonable possibility of being related to study treatment, or a study procedure, considering the disease, concomitant treatment or pathologies.

Safety data, in particular AEs, SAEs, and adverse laboratory abnormalities, will be independently assessed by the investigator, and will be considered related to the investigational product unless there is clear evidence that the event is not related.

Planned surgeries should not be reported as AEs unless the underlying medical condition has worsened during the study.

If a subject's investigational product is discontinued because of an AE, study site personnel must report this to Lilly or its designee via eCRF.

9.2.1. Serious Adverse Events

An SAE is any AE from this study that results in 1 of the following:

- death
- initial or prolonged inpatient hospitalization
- a life-threatening experience (i.e., immediate risk of dying)
- persistent or significant disability/incapacity
- congenital anomaly/birth defect
- important medical events that may not be immediately life threatening or result in death or hospitalization but may jeopardize the subject or may require intervention to prevent 1 of the other outcomes listed in the definition earlier.

Study site personnel must alert the Lilly CRP/CP, or its designee, of any SAE as soon as practically possible.

Additionally, study site personnel must alert Lilly Global Patient Safety, or its designee, of any SAE within 24 hours of investigator awareness of the event via a sponsor-approved method. If alerts are issued via telephone, they are to be immediately followed up with official notification on study-specific SAE forms. This 24-hour notification requirement refers to the initial SAE information and all follow-up SAE information.

Although all AEs are recorded in the eCRF after signing informed consent, SAE reporting to the sponsor begins after the subject has signed informed consent and has received investigational product. However, if an SAE occurs after signing informed consent, but prior to receiving

investigational product, AND is considered reasonably possibly related to a study procedure then it **MUST** be reported.

Investigators are not obligated to actively seek AEs or SAEs in subjects once they have discontinued from and/or completed the study (the subject summary eCRF has been completed). However, if the investigator learns of any SAE, including a death, at any time after a subject has been discharged from the study, and he/she considers the event reasonably possibly related to the study treatment or study participation, the investigator must promptly notify Lilly.

Pregnancy (maternal or paternal exposure to investigational product) does not meet the definition of an AE. However, to fulfill regulatory requirements, any pregnancy should be reported following the SAE process to collect data on the outcome for both mother and fetus.

9.2.1.1. Suspected Unexpected Serious Adverse Reactions

Suspected unexpected serious adverse reactions (SUSARs) are serious events that are not listed in the IB and that the investigator reports as related to investigational product or procedure. Lilly has procedures that will be followed for the recording and expedited reporting of SUSARs that are consistent with global regulations and the associated detailed guidance.

9.2.2. Complaint Handling

Lilly collects product complaints on investigational products and drug delivery systems used in clinical trials to ensure the safety of study participants, monitor quality, and to facilitate process and product improvements.

Subjects should be instructed to contact the investigator as soon as possible if he or she has a complaint or problem with the investigational product [or drug delivery system] so that the situation can be assessed.

9.3. Treatment of Overdose

For the purposes of this study, an overdose of LY3478045 is considered any dose higher than the dose assigned through randomization.

Refer to the LY3478045 IB for more details.

9.4. Safety

9.4.1. Laboratory Tests

For each subject, laboratory tests detailed in [Appendix 2](#) should be conducted according to the Schedule of Activities (Section 2) locally.

Except for safety laboratory test results that may unblind the study, Lilly or its designee will provide the investigator with the results of laboratory tests analyzed by a central vendor, if a central vendor is used for the study.

9.4.2. Physical Examination

Physical examinations and routine medical assessments including body temperature will be conducted as specified in the Schedule of Activities (Section 2) and as clinically indicated.

Subjects will be advised to wear sunglasses, hats, and sunscreen during sun exposure. During physical examination, treatment-emergent ocular and dermal photosensitivity events will also be assessed by asking the subject for any abnormal eye or skin irritation, redness, itching, burning sensation in daylight or on exposure to sunlight. The subject will be examined for abnormal skin erythema and hyperemia in exposed areas, hyperemia, scleritis, and conjunctivitis.

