Secondary To determine the pharmacokinetics of LY3478045 following single and multiple doses in healthy subjects.	AUC(0-24), AUC(0-inf), C _{max} , and t _{max} .

Abbreviations: AUC(0-24) = area under concentration versus time curve from time zero to 24 hours; AUC(0-inf) = AUC from time zero to infinity; C_{max} = maximum observed drug concentration; SAE = serious adverse event; t_{max} = time of C_{max}; TEAE = treatment-emergent adverse event.

Summary of Study Design:

Study GZKA is a Phase 1, single site, randomized, double-blind, placebo-controlled, 2-part study of LY3478045 in healthy subjects.

Part A: single-ascending dose.

Part B: multiple-ascending dose design that evaluates the potential for a drug-drug interaction.

In Part A, single-ascending oral doses of either LY3478045 or placebo will be administered in up to 5 cohorts. Each cohort will consist of at least 8 subjects, 6 subjects will receive LY3478045 and 2 subjects will receive placebo. Cohort 5 is an optional cohort that may be assessed based on the available safety and PK data from the previous 4 cohorts.

Part B will be initiated after assessing safety, tolerability, PK, and PD data through Cohort 3 in Part A.

Multiple-ascending oral doses of LY3478045 will be administered once daily for 14 days in up to 4 cohorts. Each cohort will consist of at least 8 subjects. In Cohorts 1 and 3, six subjects will receive LY3478045 and 2 subjects will receive placebo. In Cohorts 2 and 4, six subjects will receive LY3478045 followed by a single dose of **CC1** and 2 subjects will receive placebo followed by a single dose of atorvastatin **CC1** later.

Treatment Arms and Planned Duration for an Individual subject:

Treatment Name	LY3478045	Placebo	Atorvastatin
Dosage Formulation	CC1	Capsules	Tablets
Dose strength	CC1	-	40 mg
Route of Administration	Oral	Oral	Oral

The planned duration for each subject is approximately 43 days in Part A and 57 to 59 days in Part B of the study.

Number of Subjects:

Up to 50 subjects may be enrolled in Part A to ensure that at least 40 subjects complete the study (depending on whether subjects will be enrolled in optional Cohort 5). Up to 40 subjects may be enrolled in Part B to ensure that at least 32 subjects complete the study.

Statistical Analysis:

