2.1. Part A (Single-Ascending Doses)

	Screening	Days							FU ^a	ED ^b	Comments
Procedure	^c ≤28 days before Day -1	-1	1	2	3	4	5	7	14		
Informed Consent	X										
Admission to CRU		X									
Discharge from CRU						X					Subjects may be discharged on Day 5 at the discretion of the investigator.
Non-Residential Visit							X	X	X	X	
LY3478045 Administration			X								
Medical History	X										Information regarding occasional use of vitamin/mineral supplements will be taken as a part of the medical history evaluation at the time of subject screening.
Complete Physical Examination	X								X	X	Targeted PE may be conducted at other visits at the discretion of the investigator.
Height	X										
Weight	X	X									
Pregnancy Test	X	X							X	X	Serum pregnancy test will be performed at screening and urine pregnancy test will be performed at all other specified timepoints.
Blood Pressure and Pulse Rate (Supine) ^c	X	X	P, every 1 h up to 12 h postdose	24, 36 h	48 h	72 h		X	X	X	
Body Temperature	X	X							X	X	
Clinical Laboratory Tests	X	X	P	X	X			X	X		See Appendix 2 for complete list.
Serum Creatinine ^d			P, 4, 12, 24 h								
TriPLICATE 12-Lead ECG			Predose: 1.5 h, 1 h, and 30 min. Postdose: 0.5, 1.5, 2.5, 4, 6, 8,	24 h							

	Screening	Days							FU ^a	ED ^b	Comments
Procedure	≤28 days before Day -1	-1	1	2	3	4	5	7	14		
			10, 12, 16 h								
Single 12-Lead ECG	X				X				X	X	
Adverse Event Recording	X	X	X	X	X	X	X	X	X	X	
Pharmacokinetic Sampling ^d			P, 0.75, 1.5, 3, 4, 6, 8, 10, 12, 16 h	24 h	48 h	72 h	96 h				
Meal (Low Fructose)			20 min, 6, 12 h								
Fructose Beverage (for Fructose Tolerance Test)			during meal: 20 min, 6, 12 h								
Fructose Tolerance Test Assay ^d			CCI	CCI							
Genetic Sample			X								
Fasting Biomarker Samples (Nonpharmacogenetic)		X		X							
CCI			P, 0.75, 1.5, 3, 4, 8, 12, 16 h	24 h	48 h	72 h	96 h				
24-hour Urine Collection for LY3478045 and Creatinine ^d			0-12, 12-24 h	24-36, 36-48 h	48-60, 60-72 h						

Abbreviations: CRU = clinical research unit; ECG = electrocardiogram; ED = early discontinuation; FU = follow-up; h = hour(s); min = minutes; P = predose; PE = physical examination.

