7.1. Treatment Administered

LY3478045 or placebo will be administered orally with approximately 240 mL of room temperature water in the morning of each dosing day (Day 1 in SAD; Days 1 to 14 in MAD) in a sitting position. Subjects will not be allowed to lie supine for 2 hours after dosing, unless clinically indicated or for study procedures.

Table GZKA.3. Treatments Administered

Treatment Name	LY3478045	Placebo	Atorvastatin
Dosage Formulation	CC1	Capsules	Tablets
Dose strength		-	40 mg
Route of Administration	Oral	Oral	Oral

The investigator or designee is responsible for

- explaining the correct use of the investigational product(s) to the site personnel
- verifying that instructions are followed properly
- maintaining accurate records of investigational product dispensing and collection, and
- returning all unused medications to Lilly or its designee at the end of the study

Note: In some cases, sites may destroy the material if, during the investigative site selection, the evaluator has verified and documented that the site has appropriate facilities and written procedures to dispose off the clinical materials.

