8.2. Discontinuation from the Study

Subjects will be discontinued under the following circumstances:

- Enrollment in any other clinical study involving an investigational product or enrollment in any other type of medical research judged not to be scientifically or medically compatible with this study
- Participation in the study needs to be stopped for medical, safety, regulatory, or other reasons consistent with applicable laws, regulations, and good clinical practice (GCP)
 - Any TEAE or SAE considered possibly or probably related to study drug that is severe or medically significant but not immediately life threatening; or where hospitalization or prolongation of hospitalization is indicated; or is disabling; or limits self-care activities of daily living.
 - Any TEAE or SAE regardless of attribution to study drug that has life-threatening consequences or urgent intervention is indicated.
- Investigator Decision

- the investigator decides that the subject should be discontinued from the study
- if the subject, for any reason, requires treatment with another therapeutic agent that has been demonstrated to be effective for treatment of the study indication, discontinuation from the study occurs prior to introduction of the new agent
- Subject Decision
 - the subject, or legal representative, requests to be withdrawn from the study.

The replacement strategy for discontinued participants is described in Section 10.1. If deemed appropriate by the investigator, early discontinuation procedures will be performed as shown in the Schedule of Activities (Section 2).

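### The protocol's photosensitivity check is tied to a physical examination that, for a completer, is first required 13 days (Part A) or 14 days (Part B) after the last dose

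*Protocol*

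**What the plan says.** Protocol Section 9.4.2 sets up a specific check. It states: "During physical examination, treatment-emergent ocular and dermal photosensitivity events will also be assessed by asking the subject" about eye and skin symptoms on exposure to daylight, followed by an inspection for redness of exposed skin and inflammation of the eyes. The same section advises subjects to protect themselves from the sun.

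On timing, Section 9.4.2 says: "Physical examinations and routine medical assessments including body temperature will be conducted as specified in the Schedule of Activities (Section 2) and as clinically indicated". In the schedules for Part A (Section 2.1), Part B Cohorts 1 and 3 (Section 2.2) and Part B Cohorts 2 and 4 (Section 2.3), the row "Complete Physical Examination" is marked at screening, follow-up and early discontinuation, and on no other day. The comment in that row reads: "Targeted PE may be conducted at other visits at the discretion of the investigator".

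Section 7.1 gives the dosing days as "Day 1 in SAD; Days 1 to 14 in MAD". Section 8.2 makes the early discontinuation examination conditional: "If deemed appropriate by the investigator, early discontinuation procedures will be performed as shown in the Schedule of Activities". The row "Adverse Event Recording" is marked across the study days, with no photosensitivity question attached to it.

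**The concern.** The check is meant to detect treatment-emergent reactions, so at least one required occasion should fall while drug is likely to be present. For a subject who follows the schedule, none does. Skin or eye signs that have cleared by follow-up can no longer be inspected. Until then, the prompted questions are asked only if an investigator chooses to examine the subject, and that may vary between subjects and cohorts.

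Dose escalation is also affected. Section 7.4.1 requires clinical assessment and safety laboratory results up to Day 7 in six or more of the eight subjects. It does not say what the clinical assessment contains, and no required photosensitivity check falls between first dose and Day 7 in either part. Escalation can therefore proceed before any subject in the cohort has had the check that Section 9.4.2 describes. Safety and tolerability is the primary objective.

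**Working it through.** **1. Confirm the follow-up days.** The synopsis says: "The planned duration for each subject is approximately 43 days in Part A and 57 to 59 days in Part B of the study". Duration = 28 days of screening + lead-in days + follow-up day.
- Part A: 28 + 1 + 14 = 43.
- Part B, Cohorts 1 and 3: 28 + 1 + 28 = 57.
- Part B, Cohorts 2 and 4: 28 + 3 + 28 = 59.

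All three match, so follow-up is Day 14 in Part A and Day 28 in Part B.

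**2. Gap from last dose to first required check (completers).** Gap = follow-up day − last dosing day.
- Part A: 14 − 1 = 13 days (312 h).
- Part B: 28 − 14 = 14 days (336 h).

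**3. Required checks before follow-up.** The complete examination row has no mark on Days 1 to 7 in Part A or on Days 1 to 17 in Part B. The count is 0 in both parts.

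**4. Longest interval without scheduled contact before follow-up.**
- Part A: Day 7 to Day 14 = 7 days.
- Part B: Day 17 to Day 28 = 11 days.

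**5. Drug remaining at each contact.** The documents show no half-life, so this step rests on an assumption. With single-exponential decline, the share left is 100 × 0.5^(hours since last dose ÷ half-life). For example, in Part A at follow-up with a 48 h half-life: 100 × 0.5^(312/48) = 100 × 0.5^6.5 = 1.1%.

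| Contact | Hours after last dose | 12 h | 24 h | 48 h | 72 h |
|---|---|---|---|---|---|
| Part A Day 4 (discharge) | 72 | 1.6% | 12.5% | 35% | 50% |
| Part A Day 5 | 96 | 0.4% | 6.3% | 25% | 40% |
| Part A Day 7 | 144 | 0.02% | 1.6% | 12.5% | 25% |
| Part A Day 14 (follow-up) | 312 | <0.001% | 0.01% | 1.1% | 5.0% |
| Part B Day 17 (discharge) | 72 | 1.6% | 12.5% | 35% | 50% |
| Part B Day 28 (follow-up) | 336 | <0.001% | 0.006% | 0.8% | 3.9% |

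At an assumed 96 h the follow-up shares rise to 10.5% (Part A) and 8.8% (Part B). With a half-life near 12 h, little drug would remain even at the Part A outpatient visits. Their value would then lie mainly in seeing signs sooner and asking about a shorter period.

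**The case against.** The strongest reply is that reactions can be captured in other ways. Adverse events are recorded across the study days, and SAP Section 9.6.1 summarizes treatment-emergent events from that record. Targeted examinations are allowed at any visit, examinations may be done when clinically indicated, and a subject who stops early may be examined with drug present. No listed endpoint or SAP analysis uses the photosensitivity examination itself. The preclinical section and part of the benefit/risk section are blacked out, so the size of any photosensitivity risk cannot be judged here; the visible text calls the nonclinical risks low.

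Much of this stands, and it rules out several stronger readings that a reader might infer:
- **That reactions will go unrecorded, or that a conclusion of no photosensitivity would rest on the follow-up examination alone.** Adverse event recording supports neither.
- **That subjects must recall two weeks.** Scheduled contacts leave 7 or 11 days, as shown above.
- **That an inspection happens only after a complaint.** The schedule leaves targeted examination to the investigator and sets no such condition.
- **That the drug is known to be gone by follow-up.** That is an inference from assumed half-lives, and the timing of the last concentration sample does not establish it.

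What the reply does not supply is a requirement. Each of these routes permits the check or may capture a reaction; none obliges the site to ask the Section 9.4.2 questions and inspect skin and eyes during dosing or soon after it.

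**Conclusion.** The point holds as a scheduling gap in a check that the sponsor itself specified. The number of required photosensitivity checks between first dose and follow-up is zero in both parts, and a completer's first comes 13 or 14 days after the last dose. If all cohorts run as planned, this applies to 5 × 6 = 30 subjects on LY3478045 in Part A and 4 × 6 = 24 in Part B, 54 in all, less any who discontinue early.

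The calendar result needs no assumption. The statement that little drug remains at follow-up does: about 5% or less for half-lives of 12 to 72 h, and about 10% in Part A at 96 h. The change is worth making because it is cheap and makes the detection of a named safety event more uniform. The documents do not show that the present plan would miss events.

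**What to change.** Reconcile Section 9.4.2 with Section 2. Add a row to each schedule for the Section 9.4.2 questions with a targeted skin and eye inspection, and have Section 9.4.2 refer to those times as well as to the complete examination. Use existing contacts:
- **Part A:** discharge, Day 5 and Day 7. The outpatient visits are the most useful, because subjects may by then have been in daylight. The Day 7 check would also be available for the escalation decision.
- **Part B:** Day 7, Day 14 and the Day 17 discharge, so that the check falls during dosing and shortly after it.

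The Part B additions all fall on or before discharge. The amended text should therefore say that the period from Day 17 to Day 28 still relies on adverse event reporting and the follow-up questions.

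The cost is amendment wording and a few minutes per visit, with no new visit, blood sample or change to dosing. Prompted questions may raise the number of minor skin and eye complaints recorded in both arms, so rates should be read against placebo.

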9.4.2.1. Vital Signs

For each subject, vital sign measurements should be conducted according to the Schedule of Activities (Section 2).

Blood pressure and pulse rate should be measured after at least 5 minutes supine.

If orthostatic measurements are required, subjects should be supine for at least 5 minutes and stand for at least 2 minutes.

If the subject feels unable to stand, supine vital signs only will be recorded.

Unscheduled orthostatic vital signs should be assessed, if possible, during any AE of dizziness or posture-induced symptoms. Additional vital signs may be measured during each study period if warranted.

9.4.3. Electrocardiograms

For each subject, single and triplicate ECGs should be collected according to the Schedule of Activities (Section 2).

Any clinically significant findings from ECGs that result in a diagnosis and that occur after the subject receives the first dose of the investigational product should be reported to Lilly, or its designee, as an AE via eCRF.

Electrocardiograms must be recorded before collecting any blood samples. Subjects must be supine for approximately 5 to 10 minutes before ECG collection and remain supine but awake during ECG collection. Consecutive replicate ECGs will be obtained at approximately 1-minute intervals. Electrocardiograms may be obtained at additional times, when deemed clinically necessary.

Electrocardiograms will be interpreted by a qualified investigator (physician or qualified designee) at the site as soon after the time of ECG collection as possible, and ideally while the subject is still present, to determine whether the subject meets entry criteria at the relevant visit(s) and for immediate subject management should any clinically relevant findings be identified.

If a clinically significant quantitative or qualitative change from baseline is identified after enrollment, the investigator will assess the subject for symptoms (e.g., palpitations, near syncope, syncope) to determine whether the subject can continue in the study. The investigator

or qualified designee is responsible for determining if any change in subject management is needed and must document his/her review of the ECG printed at the time of evaluation from at least 1 of the replicate ECGs from each time point.

Digital ECGs will be electronically transmitted to a central ECG laboratory designated by Lilly. The central ECG laboratory will perform a basic quality control check (e.g., demographics and study details) then store the ECGs in a database. At a future time, the stored ECG data may be overread at the central ECG laboratory for further evaluation of machine-read measurements or to meet regulatory requirements.

The machine-read ECG intervals and heart rate may be used for data analysis and report writing purposes unless a cardiologist overread of the ECGs is conducted prior to completion of the final study report (in which case the overread data would be used).

